## Study Synopsis

Complete Protocol Title	Post-Market Clinical Follow-Up Study to Provide Safety, Performance and Clinical Benefits Data of the Zimmer® Plates and Screws System applied for Diaphyseal, Proximal Humerus and Proximal Tibia Fractures (Implants and Instrumentation) – A Retro-and Prospective Consecutive Series Study
Protocol Number	MDRG2017-89MS-158T
Short Protocol Title	Zimmer Plates and Screws (ZPS) System Study
Sponsor	Zimmer GmbH, Zug, Switzerland
Manufacturer	Zimmer Inc.
Study Device(s)	
ZPS System plates (implants and instrumentation) for which data is being collected within this study*:
 
 
○ Diaphysis group: 
 
➤ Compression Plate (2.0 and 2.7): 
 
➤ Compression Broad Plate: 
 
➤ Compression Narrow Plate: 
 
➤ One-Quarter Tubular Plate with Collar: 
 
➤ Cobra Head Plate: 
 
➤ Semi-Tubular Plate: 
 
➤ Straight Plate (1.5 and 2.0mm): 
 
 
 

	 
 
○ Proximal Humerus group:       
 
➤ T-Plate (4.5mm):
  
➤ Cloverleaf-Plate:
  
 
 
○ Proximal Tibia group:       
 
➤ L-Buttress Plate:
  
➤ T-Buttress Plate:
  
➤ Spoon Plate:
  
 
 
 
* Plates are grouped per anatomical region they are applied.

Technical Documentation Reference Number	414b, 402a, 401, 850
Study Objectives/Endpoints	
The objective of this post-market clinical follow-up (PMCF) study is to collect data confirming safety, performance and clinical benefits of the Zimmer Plates and Screws System (implants and instrumentation) when used to stabilize diaphyseal, proximal humerus and proximal tibia fractures.
 
The primary objective is the assessment of performance by analyzing fracture healing.
 
The secondary objectives are the assessment of safety by recording and analyzing the incidence and frequency of complications and adverse events. Relation of the events to implant, instrumentation and/or procedure should be specified. Subjects' outcomes will also be assessed.

Indications/Target Population	Consecutive series of subjects implanted with plates and screws belonging to the ZPS System according to the indications for use. Please refer to the study device section of this synopsis for more details on the different plates used in this study. Inclusion/exclusion criteria are based on the indications and contraindications in the Instruction for Use (IFU).
Inclusion/Exclusion Criteria	
The inclusion criteria are:
 
Patients having received one of the plates belonging to the ZPS System, designed for temporary internal fixation to stabilize fractures during the normal healing process.
 
In this study we will collect data specifically on ZPS plates belonging to the Diaphysis, Proximal Humerus and Proximal Tibia groups.
 
The exclusion criteria are:
 
 
• Off-label use
 
• Patients under the age of 18
 
• Prisoners
 
• Severely comminuted fractures in which bone fragments are too small or numerous to adequately fix or maintain a reduced position.
 
• Infection.
 
• Metal sensitivity or intolerance.
 
• Severe osteopenia and/or osteoporosis, or in the presence of marked or rapid bone absorption, metabolic bone disease, cancer, or any other tumor-like condition of the bone which may compromise fixation.
 
• Sternal or spinal fractures.
 
• Anatomical location in which the device would interfere with nerves, blood vessels, or other vital structures.
 
• Patients with inadequate soft tissue coverage at the implant site.
 

Study Design	Single-Center, Retro- and prospective, Non-controlled, Non-randomized, Consecutive series of patients
Clinical Phase	Post-market
Sample Size	
The goal is to collect data on a total of 112 consecutive cases operated with a plate belonging to one of the three ZPS System groups defined in this synopsis and distributed as following:
 
 
• 50 consecutive cases treated with a plate of the Diaphysis group.
 

	
 
• 52 consecutive cases treated with a plate of the Proximal Humerus group.
 
• 10 consecutive cases treated with a plate of the Proximal Tibia group.
 
 
The cases should be equally distributed between the different plates of each group, if possible.

Length of Study	
18 months overall:
 
 
• Ethics Committee approval
 
• Subject identification, consent and enrollment into the study
 
• Collection of baseline and follow-up (FUP) information available in medical notes from the pre-operative condition to the immediate post-op and last consultation visit
 
• Conduct FUP phone call
 
• Conduct data collection, analyses, write an interim report as well as a final report or a manuscript.
 

Materials and Methods	Retrospective data will be collected from medical charts including baseline information from the preoperative, operative, immediate post-operative interval and last consultation visit. In addition, a prospective FUP call (min 1 year post-op) will be performed. All data will be entered into an Excel database provided by the Sponsor.
Data Collection	Paper/Electronic
Statistical Reporting	Statistical analysis will be conducted by Zimmer Biomet or its designee. Data collected in the study will be summarized descriptively. Descriptive summaries will be the basis of study reports to participants, as well as to generate an overall summary of the clinical and radiological evaluation of the ZPS System groups described in this protocol. Continuous data (e.g. age) will be summarized through means, medians, standard deviation, minimum, maximum and 95% confidence intervals (CIs) over time periods of interest. Categorical data (e.g. gender) will be summarized using counts, percentages and 95% confidence limits over time periods of interest. Summaries of fracture healing rate and complication data will be presented as frequencies and percentages. Subgroup summaries will be generated as needed either by strata within the study population (e.g. male vs. female) or by different cut-points (e.g. body mass index (BMI)) ranges.
Scores/Performance Assessments	Tegner and Lysholm (Proximal Tibia Group), Oxford Shoulder Score (Proximal Humerus Group), EQ-5D-5L (Diaphysis Group); Fracture Healing, Adverse Events

Standards	
The PMCF is compliant with the below:
 
 
• ISO 14155: 2020 - Clinical investigation of medical devices for human subjects - Good clinical practice [1].
 
• The Declaration of Helsinki (DoH) - Ethical principles for medical research involving human subjects [2].
 
• European Regulation (EU) 2017/745 [3].
 
• MDCG 2020-10/1 Safety reporting in clinical investigations for medical devices under the Regulation (EU) 2017/74 [4]
 

Study Funding	
Funding for this clinical study is made available by Zimmer Biomet to support clinical data collection, IRB/EC review fees and other expenses associated with the conduct and execution of this study protocol as outlined in the fully executed Clinical Trial Agreement.

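### The performance objective covers instrumentation, but no pre-specified measure reflects instrument function, and harm-free malfunctions are not a required data item

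*Combined protocol and SAP*

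**What the plan says.** All references are to the Study Synopsis.

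- **Scope of the objective.** The Study Objectives/Endpoints row aims to confirm safety, "performance and clinical benefits of the Zimmer Plates and Screws System (implants and instrumentation"). The title also names instrumentation, and the Study Device(s) row describes "ZPS System plates (implants and instrumentation) for which data is being collected within this study".
- **How performance is assessed.** The same objectives row states: "The primary objective is the assessment of performance by analyzing fracture healing".
- **Where instrumentation is recorded.** The secondary objective is "the assessment of safety by recording and analyzing the incidence and frequency of complications and adverse events", followed by "Relation of the events to implant, instrumentation and/or procedure should be specified".
- **Listed assessments.** The Scores/Performance Assessments row names Tegner and Lysholm, the Oxford Shoulder Score and EQ-5D-5L, each for one plate group, and then "Fracture Healing, Adverse Events".
- **Who enters.** The inclusion criterion is "Patients having received one of the plates belonging to the ZPS System". The target population is "Consecutive series of subjects implanted with plates and screws belonging to the ZPS System".
- **Source and reporting.** Materials and Methods has the site read the charts, including the operative period, into an Excel database supplied by the sponsor. Statistical Reporting plans counts and percentages for healing and complications, and 95% confidence limits for categorical data in general.

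**The concern.** Fracture healing depends on the plate, the bone, the reduction and the patient. A fracture can heal after a driver has broken or a stripped screw has been exchanged, and it can fail to heal when every instrument worked. Healing therefore says little about the instruments, although the objective asks for their performance to be confirmed.

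The attribution of events to instrumentation serves the safety objective. It starts from an event that someone has already recorded. If the instrument problem caused no harm, nothing in the synopsis requires a record of it.

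Entry also depends on the operation having ended with a ZPS plate in the patient. An attempt that was given up in favour of another system is a plain intra-operative performance failure, and it would not be in the series.

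What is at stake is the interpretation of the report. Few or no instrument-related events could be taken as evidence that the instruments perform well, when no planned item was designed to show otherwise.

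**Working it through.** The point concerns coverage, and no figure in the plan is in dispute. The first two steps compare the text with itself. The last two size what follows from it.

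**1. Listed assessments against instrument function**

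| Assessment | What it measures | Instrument function? |
|---|---|---|
| Tegner | Patient score, proximal tibia | No |
| Lysholm | Patient score, proximal tibia | No |
| Oxford Shoulder Score | Patient score, proximal humerus | No |
| EQ-5D-5L | Patient score, diaphysis | No |
| Fracture healing | Result of plate, bone and surgery together | No |
| Adverse events | Recorded events, with attribution | Only through an event |

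None of the six measures instrument function directly. Complications, named in the secondary objective, work in the same way as adverse events: they are counted and attributed once recorded.

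**2. Which intra-operative problems would reach the report**

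- Instrument problem leading to an adverse event or recorded complication: counted and attributable to instrumentation.
- Instrument malfunction or screw exchange without harm: counted only if it is in the operative note and is classed as a complication. The synopsis does not define that term, so this rests on the abstractor's judgement.
- One ZPS plate given up and another ZPS plate implanted: the patient qualifies, but no item requires the change to be recorded.
- ZPS fixation given up with no ZPS plate left in place: not eligible.

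**3. Attempts outside the series**

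The planned total is 50 + 52 + 10 = 112 implanted cases. If a proportion a of attempted fixations ended without a ZPS plate, 112 implanted cases would come from 112/(1 − a) attempts. The documents give no value for a, so the range below is an assumption.

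- a = 1%: 112/0.99 = 113.1 attempts, about 1 outside the series
- a = 3%: 112/0.97 = 115.5 attempts, about 3 outside
- a = 5%: 112/0.95 = 117.9 attempts, about 6 outside

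These cases are additional to the 112 and are not a share of them.

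**4. What an added item could show**

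If a malfunction item were recorded and no malfunction were found in n cases, the exact two-sided 95% upper limit would be 1 − 0.025^(1/n).

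- All 112 cases: 3.2%
- Diaphysis, n = 50: 7.1%
- Proximal humerus, n = 52: 6.8%
- Proximal tibia, n = 10: 30.8%

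Even a clean record would leave a wide margin in the smallest group, which is why the interval should be reported with the count. These limits also assume complete recording.

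**The case against.** The strongest reply is that complications are a category in their own right. They are counted, they are attributable to instrumentation, and nothing in the synopsis limits them to patient harm. Since operative records are read, a broken instrument or stripped screw could be entered and counted. This stands. A reader might infer that harm-free failures have no place in the data, or that none would be recorded; the documents do not show that. They show only that no item requires such a record.

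Three further limits are fair:

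- A reader might infer that healing is the only performance assessment. The Scores/Performance Assessments row also lists scores and adverse events, although none of them measures instrument function.
- A reader might infer that every abandoned ZPS plate is lost. Only operations that ended with no ZPS plate in place are outside. Conditioning on implantation is also natural for a healing endpoint, because healing under a ZPS plate cannot be assessed where there is none.
- The text available is a synopsis. The database fields and event definitions are not shown, and the Standards row cites a device investigation standard and a safety-reporting guidance whose content is not reproduced. A device-deficiency item elsewhere cannot be ruled out.

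It can also be said that nothing in the plan states that an absence of events will be read as proof of instrument performance. That is true; the misreading is a risk and not a stated intention. None of these replies supplies a measure of instrument function to match the objective.

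**Conclusion.** The concern holds as a mismatch between objective and measurement. The synopsis includes instrumentation in the performance it sets out to confirm, yet none of its six listed assessments reflects instrument function, and its only instrument-related entry is the attribution of recorded events. Harm-free malfunctions and screw exchanges are not required data, and fixations abandoned without a ZPS plate are outside entry. Followed as written, the plan can support a conclusion on instrument-related complications and adverse events but not one on instrument performance.

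The size is one unsupported component of the objective; the healing and safety summaries for implanted cases stand. The number of problems missed cannot be stated, because the documents give no malfunction or abandonment rate. It would also be wrong to express abandoned fixations as a share of the 112, since they lie outside it.

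The conclusion assumes that no device-deficiency item exists in protocol text or database fields beyond the synopsis. If one does, the synopsis need only refer to it and plan its summary.

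**What to change.** One of two changes is enough.

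**Measure it.** For the 112 included cases, add a per-case intra-operative item to the Excel database, taken from the operative record: instrument breakage or malfunction, screw stripping or exchange, and unplanned change of plate. Report each per plate group as count, percentage and 95% confidence interval, whether or not harm followed. Label the result a lower bound, because operative notes under-report harmless problems. State that the results apply only to operations in which a ZPS plate was implanted. The cost is a few columns filled from notes the site is already reading.

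**Or narrow the claim.** Remove instrumentation from the performance objective and limit the conclusion on it to related complications and adverse events. The cost is wording only.

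Extending the case definition to abandoned fixations is not recommended. Those operations are not in the series, so finding them would need a separate retrospective screen of other fracture operations and a second denominator. The statement of scope deals with the gap at no such cost.

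### Does asking for consent after surgery, and for balance between plates, undermine the 112 consecutive cases?

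*Combined protocol and SAP*

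**What the plan says.** All of the relevant text is in the Study Synopsis.

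- **Sample Size:** "The goal is to collect data on a total of 112 consecutive cases operated with a plate", split into 50 Diaphysis, 52 Proximal Humerus and 10 Proximal Tibia cases. The same row adds: "The cases should be equally distributed between the different plates of each group, if possible".
- **Inclusion/Exclusion Criteria:** entry is worded for people already operated on, "Patients having received one of the plates belonging to the ZPS System". Neither consent nor being reachable appears among the criteria.
- **Length of Study:** "18 months overall", followed by a list of activities that includes "Subject identification, consent and enrollment into the study", then collection of chart data, the phone call, analysis and reports.
- **Materials and Methods:** data up to the last consultation come from charts, and "a prospective FUP call (min 1 year post-op) will be performed".
- **Statistical Reporting:** "Summaries of fracture healing rate and complication data will be presented as frequencies and percentages". The sentences before it provide 95% confidence limits for categorical data in general, which can be read to cover healing.
- **Study Objectives/Endpoints:** the purpose is to "collect data confirming safety, performance and clinical benefits", with fracture healing as the primary objective.

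**The concern.** In a study with no control group and no randomization, taking cases in unbroken order is the main protection against selection. Two features seem to weaken it.

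First, consent is listed before chart collection, while the patients already carry the plate. The timetable makes this the usual situation: a call at least 12 months after surgery has to fit into 18 months. If entry depends on that consent, patients who died, moved away or refused may be missing. Those with a poor result may refuse or seek care elsewhere; those who healed without trouble may be harder to trace. The direction of any error is therefore open.

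Second, cases taken strictly in order follow the plates the surgeons actually used. Balancing the plates would mean passing some cases over, and no order of precedence is stated.

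The synopsis gives no surgery-date start point, no count of eligible cases and no rule for cases passed over. There is no success threshold, so the descriptive healing and complication rates are themselves the result. A reader would not know what share of eligible patients they represent.

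**Working it through.** **The plan's own figure.** 50 + 52 + 10 = 112, so the total reproduces. The synopsis states no significance level, power, healing rate or dropout, so there is no further design calculation to check.

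**Timing.** 18 − 12 = 6. A patient operated on after study start can reach the call only if surgery falls in about the first 6 months, less time for approval and reporting. That most operations precede consent is an inference from this.

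**Cases left out (entry share c is assumed).** Eligible cases needed = 112/c.

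| c | Eligible | Not entered |
|---|---|---|
| 0.9 | 124.4 | 12.4 |
| 0.8 | 140 | 28 |
| 0.7 | 160 | 48 |
| 0.6 | 186.7 | 74.7 |

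**Shift in the healing rate (all inputs assumed).** With 95% healed among those entered and a share q healed among the rest, the rate in all eligible cases is c × 0.95 + (1 − c) × q. The overstatement is (1 − c) × (0.95 − q).

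- c = 0.7, q = 0.80: 0.3 × 0.15 = 4.5 points over.
- c = 0.7, q = 0.90: 0.3 × 0.05 = 1.5 points over.
- c = 0.7, q = 1.00: 0.3 × (−0.05) = 1.5 points under.
- q = 0.80 at other entry shares: 1.5 points at c = 0.9, 3.0 at c = 0.8 and 6.0 at c = 0.6.
- q = 0.50, a harsh case: 4.5 points at c = 0.9, 9.0 at c = 0.8 and 13.5 at c = 0.7.
- q = 0.95: no shift at any c.

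**Sampling error for scale.** The half-width is 1.96 × √(0.95 × 0.05/n): 4.0 points at n = 112, 6.0 at n = 50, 5.9 at n = 52 and 13.5 at n = 10. The normal approximation is rough at this rate. At n = 50 and n = 52 the upper limit already exceeds 100%, and at n = 10 the approximation is poor.

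At 70% entry, only the most adverse of the first three cases reaches the whole-series half-width; the other two are well below it. Harsher assumptions give larger shifts. The documents do not favor any of these cases.

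**Balance between plates.** The synopsis lists 7, 2 and 3 plates in the three groups, 12 in all. Equal shares would be 50/7 = 7.1, 52/2 = 26 and 10/3 = 3.3 cases per plate. If 26 each were a fixed quota in Proximal Humerus, operations needed = 26/(share of the less used plate):

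- 40% share: 65 operations, 13 passed over.
- 30% share: 86.7 operations, 34.7 passed over.
- 20% share: 130 operations, 78 passed over.

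The text sets no such quota, so these figures are upper limits for each assumed share. Passing over by plate type is also not selection on outcome. If cases are taken in order within each plate, the plate-level rates are not distorted by it; only the mix of plates behind the group rate changes.

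**The case for a change.** The strongest case for a change is that consecutive order appears in the title, target population, design and every group target, yet the synopsis gives no way to verify it. A confidence interval measures sampling error and says nothing about selection. The remedy would be cheap: a start date, a log of eligible cases with reasons for non-entry, and entered over eligible shown beside each rate. Even if consent were waived for chart data, the start point and the priority between consecutive order and plate balance would still be unstated in the text at hand.

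Much of this stands as good reporting practice. The risk is plausible, and a single-center team would do well to keep such a log. It falls short of a fault in the plan for three reasons.

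- The harm depends on three steps that the documents do not supply: that entry requires consent, that many patients are lost by it, and that they healed differently.
- What is said to be missing is operational detail, and only a synopsis is available. The protocol body may already contain it.
- The added count would inform readers but would alter no healing or complication rate. Best- and worst-case bounds would help little: at 70% entry and 95% healed they run from 0.7 × 0.95 = 66.5% to 0.7 × 0.95 + 0.3 = 96.5%.

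Ranking consecutive order above plate balance has its own cost, because some of the 12 plates might then have very few cases. Counting chart-only patients toward the targets would leave fewer with call data, which matters most among the 10 tibia cases.

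**Conclusion.** No change to the plan is needed. The mention of consent is an item in a list of activities, and the entry criteria do not make it a condition for using chart data. The missing start date, log and consent route are details that a study team settles in the full protocol or in conduct. The request for balance is qualified and can be read as yielding to consecutive order; how far to pursue it is a fair trade-off between an unbroken series and coverage of each plate.

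The size of any bias is unknown in both amount and sign. In the 70% entry illustration it runs from 1.5 points under to 4.5 points over as healing among the rest falls from 100% to 80%. It is larger under harsher assumptions and zero if those not entered healed equally well. All of these inputs are assumed. The conclusion rests on reading a synopsis as a synopsis and on the analysis being descriptive with no stated threshold. It would need another look if the full protocol made post-operative consent a condition of entry and kept no record of those left out.
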